4. STATISTICAL ANALYSES

4.1. General Considerations

In general, all primary, secondary, and other analyses will be performed on the Full Analysis Set.

4.1.1. General Methodology

Participants who prematurely withdrew from study will not be replaced.

Unless otherwise specified, continuous data will be summarized using descriptive statistics: n, mean, standard deviation (SD), median, minimum and maximum. Categorical data will be summarized as the number and percentage of participants in each category.

95% confidence interval (CI) for proportion will be based on exact Clopper-Pearson confidence interval. [[Clopper](#), 1934]

95% CI for relative risk will be based on Wald confidence interval [[Woolf](#), 1955; [Haldane](#), 1956].

For a given participant, missing or non-evaluable measurements will neither be imputed nor be replaced, and therefore will not be included in analysis.

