9.3. Statistical analyses

9.3.1. General considerations

All statistical analyses are descriptive. Besides the primary analyses, sub-group analyses may be conducted.

All primary and secondary analyses will be performed on the ***Full Analysis Set***.

9.3.2. **Primary endpoints analysis**

	Primary Endpoints	Statistical Analysis Methods
Maternal participants	Number and percentage of maternal participants reporting pregnancy outcomes and pregnancy related AESIs within the first pregnancy conceived within 2 years post-vaccination in participants enrolled in prior RSV MAT studies up to Day 42 post-delivery.	The number and percentage of maternal participants reporting pregnancy outcomes and pregnancy related AESIs within the first pregnancy conceived within 2 years post-vaccine/control will be tabulated with its exact 95% CI by study arms. By participant listings of pregnancy related outcomes and AESIs will be prepared
Infant participants	Number and percentage of infant participant reporting infant AESIs from the first pregnancy conceived within 2 years post-vaccination in participants enrolled in prior RSV MAT studies up to Day 42 post-delivery.	The Number and percentage of infant participant reporting infant AESIs from the first study pregnancy conceived within 2 years post-vaccine/control will be tabulated with its exact 95% CI by study arms. By participant listings of infant AESIs will be prepared.

Pregnancy outcomes include (not limited to) spontaneous abortion, stillbirth, and preterm birth. The pregnancy related adverse events of special interest (AESIs) and infant AESIs are listed in Section 8.4.5.1.

9.3.3. **Secondary endpoints analyses**9.3.3.1. **Pregnancy outcomes and AESIs from any study pregnancy**

	Secondary Endpoints	Statistical Analysis Methods
Maternal participants	Number and percentage of maternal participants reporting pregnancy outcomes and pregnancy related AESIs during any study pregnancy conceived within 2 years post-vaccination in participants enrolled in prior RSV MAT studies up to Day 42 post-delivery.	The number and percentage of maternal participants reporting pregnancy outcomes and pregnancy related AESIs during any pregnancy conceived within 2 years post-vaccination in participants enrolled in prior RSV MAT studies up to Day 42 post-delivery , will be tabulated with its exact 95% CI by study arms on subject level. By participant listings of pregnancy related outcomes and AESIs will be prepared.

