4.2.1. Definition of primary endpoints

The first pregnancy during study period is defined as the first pregnancy conceived post-vaccination or control in participants enrolled in RSV MAT studies (those previously received RSVPreF3 or control) up to Day 42 post-delivery.

Pregnancy outcomes include (not limited to):

1. Live birth
2. Spontaneous abortion

3. Stillbirth
4. Elective/therapeutic termination
5. Live birth Congenital anomaly(ies)
6. Spontaneous abortion Congenital anomaly(ies)
7. Fetal death/still birth Congenital anomaly(ies)
8. Elective/therapeutic termination Congenital anomaly(ies)

| Pregnancy-related AESIs | Infant AESIs |
|---|--|
| 
 • Hypertensive disorders of pregnancy: 
 – gestational hypertension, – pre-eclampsia, – pre-eclampsia with severe features including eclampsia; • Fetal growth restriction; • Pathways to preterm birth: 
 – premature preterm rupture of membranes, – preterm labor, – insufficient cervix – provider-initiated preterm birth; • Gestational diabetes mellitus; and • Chorioamnionitis. | 
 • Small for gestational age, • Low birth weight including very low and extremely low birth weight (<2500 g, <1500 g, <1000 g), • Congenital anomalies: 
 – major external structural defects, – internal structural defects, – functional defects, • Neonatal death 
 – in a non-viable live birth [<22 weeks gestation] – in an extremely pre-term birth [22.GA<28 weeks], – in a preterm live birth [28.GA<37 weeks], – in a term live birth, • Preterm birth |

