4.2.2. Main analytical approach

All primary analyses will be performed on the Full Analysis Set.

Main primary analyses in maternal participants will include summaries of pregnancy outcomes and pregnancy related AESIs overall and by study arms. Pathways to preterm birth will be further broken down as: extremely preterm births (GA at birth: < 28 weeks); very preterm births (GA at birth: 28 - < 32 weeks); moderate to late preterm births (32 - < 37 weeks).

Main primary analyses in infant participants will include summaries overall, by study arms and by gestational age at birth (≥ 37 weeks or < 37 weeks; overall) of infant AESIs.

Primary endpoints will be reported by study arms while stratified by **CCI**

Pregnancy outcomes analytical approach:

The number and percentage of each pregnancy outcome is calculated among the maternal Full Analysis Set (for participants with medical records available), per pregnancy regardless of the number of fetuses in the concerned pregnancy.

The pregnancy related adverse events of special interest (AESIs) analytical approach:

The number and percentage of each pregnancy related adverse event of special interest is calculated based on the number of pregnancies reporting the symptom at least once. In addition, we will report the occurrence of pregnancy related adverse events of special interest. Only pregnancies based on medical record collection will be considered.

For infant participants, the infant participant reporting AESIs analytical approach:

The number and percentage of each neonatal adverse event of special interest is calculated based on the number of infants reporting the symptom at least once. In addition, we will report the occurrence of neonatal adverse events of special interest. Infants' data based on medical records only, will be considered.

CCI

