4.3.1.2. Main analytical approach

Refer to Section 4.2.2. All secondary analyses will be performed on the Full Analysis Set.

Main secondary analyses in maternal participants will include summaries of pregnancy outcomes and pregnancy related AESIs overall and by study arms. Pathways to preterm birth will be further broken down as: extremely preterm births (GA at birth: < 28 weeks); very preterm births (GA at birth: 28 - < 32 weeks); moderate to late preterm births (32 - < 37 weeks).

Main secondary analyses in infant participants will include summaries overall, by study arms and by gestational age at birth (≥ 37 weeks or < 37 weeks; overall) of infant AESIs.

Secondary endpoints will be reported by study arms while stratified by CCI

Pregnancy outcomes analytical approach:

The number and percentage of each pregnancy outcome is calculated among all pregnancies (for pregnancies with medical records available), per event regardless of the number of fetuses in the concerned pregnancy.

The pregnancy related adverse events of special interest (AESIs) analytical approach:

The number and percentage of each pregnancy related adverse event of special interest is calculated based on the number of pregnancies reporting the symptom at least once. In addition, we will report the occurrence of pregnancy related adverse events of special interest. Only pregnancies based on medical record collection will be considered.

For infant participants, the infant participant reporting AESIs analytical approach:

The number and percentage of each neonatal adverse event of special interest is calculated based on the number of infants reporting the symptom at least once. In addition, we will report the occurrence of neonatal adverse events of special interest. Infants' data based on medical records only, will be considered.

CCI

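### Infant-level preterm birth is given intervals that treat co-twins as independent, so they are likely to be somewhat too narrow

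*SAP*

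**What the plan says.** SAP 4.1.1 sets one interval method for every percentage: "95% confidence interval (CI) for proportion will be based on exact Clopper-Pearson confidence interval". For ratios, "95% CI for relative risk will be based on Wald confidence interval".

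The counting unit depends on the endpoint:
- **Infant AESIs**, for both first and any pregnancy, are "calculated based on the number of infants reporting the symptom at least once" (SAP 4.2.2; the same rule is in 4.3.1.2). SAP 4.2.1 lists preterm birth in this group.
- **First-pregnancy outcomes** are counted "per pregnancy regardless of the number of fetuses in the concerned pregnancy" (SAP 4.2.2), which gives one record per woman.
- **Any-pregnancy outcomes**: "The number and percentage of each pregnancy outcome is calculated among all pregnancies (for pregnancies with medical records available), per event" (SAP 4.3.1.2). Any-pregnancy maternal AESIs are "calculated based on the number of pregnancies reporting the symptom at least once".
- **Protocol 9.3.3.1** says of the any-pregnancy maternal endpoint that it "will be tabulated with its exact 95% CI by study arms on subject level". The table in SAP 4.3.1 also speaks of maternal participants.

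Multiple gestation is not an exclusion (Protocol 5.1, 5.2). It is a candidate risk factor in SAP 4.3.2.2 and a planned subgroup in SAP 4.6.2.1. Relative risks with intervals and p-values are promised in SAP 4.3.2.2. The visible text has no robust variance, GEE or other provision for clustering, and the optional logistic regression in SAP 4.6.1 mentions covariates only.

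**The concern.** Clopper-Pearson and Wald intervals take their variance from independent Bernoulli units. Two infants from one delivery are not independent. For preterm birth the dependence is close to complete, because co-twins share gestational age at birth. If twins are also preterm more often than singletons, a few twin deliveries supply a disproportionate share of the events, always in pairs, and the per-infant percentage varies more than the binomial allows.

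Preterm birth is the signal behind this study (Protocol 2.2). The study tests no hypotheses, so readers will judge any difference between arms mainly from the intervals, and from the relative risks in SAP 4.3.2.2. Intervals that are too narrow would make a chance imbalance look better established than it is. Subject-level counting would not cure this for infants, because each twin is a separate infant subject.

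**Working it through.** **1. The plan's own precision figures.** Clopper-Pearson limits from beta quantiles give 2.83-8.11% for 15/300, matching the stated 2.8-8.1%. At exactly 5% of 650 they give 3.46-6.97%, matching the stated 3.5-7%; the printed count of 33/650 gives 3.52-7.06%. These figures are sound for independent participants.

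**2. Inputs for the twin check.** From the documents: a reference rate of 5% (the lowest rate in a MAT-009 group) and about 650 women with a study pregnancy (SAP 5). Assumed, because the documents are silent: arms of 433 and 217 mothers (650 split 2:1), twin share f of 1.5-3%, twin preterm rate q of 30-60%, and both twins sharing preterm status.

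**3. Design effect for preterm birth per infant.** With singleton rate s:
- infants per mother: M = 1 + f
- infant-level rate: p = [(1 - f)s + 2fq] / M
- V = (1 - f)[s(1 - p)² + (1 - s)p²] + 4f[q(1 - p)² + (1 - q)p²]
- DEFF = V / [M p(1 - p)]

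Low end (f = 0.015, q = 0.30): p = (0.04925 + 0.009)/1.015 = 0.0574; V = 0.0630; DEFF = 0.0630/(1.015 × 0.0574 × 0.9426) = 0.0630/0.0549 = 1.15.

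High end (f = 0.03, q = 0.60): p = (0.0485 + 0.036)/1.03 = 0.0820; V = 0.1081; DEFF = 0.1081/(1.03 × 0.0820 × 0.9180) = 0.1081/0.0776 = 1.39.

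The interval should be wider by about √DEFF: √1.15 = 1.07 and √1.39 = 1.18, that is 7-18%.

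**4. Simulation of the planned intervals** (40,000 replicates, s = 5%, true relative risk 1). A second run agreed to within half a percentage point.

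| Twin pregnancies | Twins preterm | DEFF | Coverage, n = 433 / n = 217 | Wald RR rejects |
|---|---|---|---|---|
| none | - | 1.00 | 96.6% / 97.1% | 4.2% |
| 1.5% | 30% | 1.15 | 94.2% / 95.8% | 6.0% |
| 1.5% | 60% | 1.25 | 93.7% / 93.4% | 7.3% |
| 3% | 30% | 1.26 | 93.5% / 93.0% | 7.3% |
| 3% | 60% | 1.39 | 92.1% / 91.8% | 9.2% |

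**5. If twins have the singleton rate.** DEFF reduces to 1 + 2f/(1 + f): 1.03 at f = 1.5%, 1.06 at 3% and 1.10 at 5%. Coverage is then about 95-96%, because Clopper-Pearson is conservative to begin with.

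**6. Repeat pregnancies.** With a share g of women having two pregnancies and intra-mother correlation ρ, DEFF = 1 + 2gρ/(1 + g). For g = 5-20% and ρ = 0.1-0.4 (assumed) this runs from 1 + 0.01/1.05 = 1.01 to 1 + 0.16/1.20 = 1.13. Simulated coverage is about 94.3-96.4%.

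**7. What it would look like.** For 15/300, Clopper-Pearson on the effective sample size moves 2.8-8.1% to 2.7-8.4% at DEFF 1.14 and to 2.5-8.8% at DEFF 1.38.

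**The case against.** The best reply is that the effect is small, rests on assumed inputs, and is partly covered already.

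- **Inputs.** No twin rate, twin preterm rate or arm split is given for this study; the only split illustrated is 100 of 300 in the RSVPreF3 group. At the mild end coverage is about nominal. This stands, so the size is a range and not a finding about the data.
- **Per-pregnancy views exist.** Protocol 9.3.2 names preterm birth among pregnancy outcomes, and SAP 4.2.2 counts pathways to preterm birth per pregnancy and splits them by gestational age at birth. For first pregnancies those units are independent. The multiple-gestation subgroup also separates singletons. This stands in part: SAP 4.2.1 still lists preterm birth itself as an infant AESI, and its per-infant interval remains as planned.
- **Descriptive study.** Relative risks and p-values appear only in the secondary risk-factor analysis, and the test behind the p-values is not named. This stands: the harm is overstated precision, not a failed primary test.
- **Redaction.** The sensitivity-analysis sections fall in blacked-out text, so a clustered or singleton analysis there cannot be excluded. The visible main analysis has none.

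A reader might also infer an undeclared departure from the protocol, because SAP 4.3.1.2 counts pregnancies where Protocol 9.3.3.1 counts subjects. The documents do not support that charge: the SAP version history announces separate calculation methods for first and any pregnancy, and SAP 4.8 is partly redacted. What remains is an inconsistency of unit.

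**Conclusion.** The point holds for infant-level endpoints, above all preterm birth. The planned intervals ignore twin dependence and are somewhat too narrow whenever twins are preterm clearly more often than singletons. Under the stated assumptions the shortfall in coverage runs from none to about 3 percentage points below 95%, and the null rejection rate of the relative risk is about 6-9%.

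Three stronger readings are not supported:
- **All any-pregnancy percentages are materially too narrow.** Repeat pregnancies alone leave coverage close to 95%, and under subject-level counting the issue disappears for mothers.
- **The primary maternal endpoints are affected.** They have one record per woman.
- **SGA, low birth weight and neonatal death are affected to the same degree.** Those endpoints were not computed, and the shared-gestational-age argument does not carry over directly to SGA or death.

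The mechanism is certain from the text. The size is moderately certain at best, because it depends on the twin rate and the twin preterm rate. This is a correction worth making, not a flaw that invalidates the analysis.

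**What to change.** In SAP 4.1.1:
- For infant-level proportions, use an exact interval on the effective sample size (Korn-Graubard) with the mother as cluster. In simulation under these assumptions it restores coverage to about 96%.
- For infant-level relative risks in SAP 4.3.2.2, use modified-Poisson GEE with robust variance clustered on the mother, and take the p-value from the same model.
- Apply the same methods to the any-pregnancy endpoints, for consistency rather than because the effect there is large.

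Show preterm birth per pregnancy for the first pregnancy beside the per-infant figure; there the units are independent.

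Separately, reconcile the unit of the any-pregnancy maternal endpoint: subject level in Protocol 9.3.3.1 and participants in the SAP 4.3.1 table, against pregnancies or events in SAP 4.3.1.2. State the chosen unit in both documents.

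The cost is SAP wording, a few lines of code and slightly wider intervals. No new data are needed.

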4.1.2. Baseline Definition

Not applicable for this study.

4.2. Primary Endpoint(s) Analyses

| | Primary Endpoints | Statistical Analysis Methods |
|------------------------------|---|--|
| Maternal participants | Number and percentage of maternal participants reporting pregnancy outcomes and pregnancy related AESIs within the first pregnancy conceived within 2 years post-vaccination and up to Day 42 post-delivery. | The number and percentage of maternal participants reporting pregnancy outcomes and pregnancy related AESIs within the first pregnancy conceived within 2 years post-vaccine/control and up to Day 42 post-delivery will be tabulated with its exact 95% CI by study arms. By participant listings of pregnancy related outcomes and AESIs will be prepared |
| Infant participants | Number and percentage of infant participant reporting infant AESIs from the first pregnancy conceived within 2 years post-vaccination and up to Day 42 post-delivery. | The Number and percentage of infant participant reporting infant AESIs from the first study pregnancy conceived within 2 years post-vaccine/control and up to Day 42 post-delivery will be tabulated with its exact 95% CI by study arms. By participant listings of infant AESIs will be prepared. |

4.2.1. Definition of primary endpoints

The first pregnancy during study period is defined as the first pregnancy conceived post-vaccination or control in participants enrolled in RSV MAT studies (those previously received RSVPreF3 or control) up to Day 42 post-delivery.

Pregnancy outcomes include (not limited to):

1. Live birth
2. Spontaneous abortion

3. Stillbirth
4. Elective/therapeutic termination
5. Live birth Congenital anomaly(ies)
6. Spontaneous abortion Congenital anomaly(ies)
7. Fetal death/still birth Congenital anomaly(ies)
8. Elective/therapeutic termination Congenital anomaly(ies)

| Pregnancy-related AESIs | Infant AESIs |
|---|--|
| 
 • Hypertensive disorders of pregnancy: 
 – gestational hypertension, – pre-eclampsia, – pre-eclampsia with severe features including eclampsia; • Fetal growth restriction; • Pathways to preterm birth: 
 – premature preterm rupture of membranes, – preterm labor, – insufficient cervix – provider-initiated preterm birth; • Gestational diabetes mellitus; and • Chorioamnionitis. | 
 • Small for gestational age, • Low birth weight including very low and extremely low birth weight (<2500 g, <1500 g, <1000 g), • Congenital anomalies: 
 – major external structural defects, – internal structural defects, – functional defects, • Neonatal death 
 – in a non-viable live birth [<22 weeks gestation] – in an extremely pre-term birth [22.GA<28 weeks], – in a preterm live birth [28.GA<37 weeks], – in a term live birth, • Preterm birth |

4.2.2. Main analytical approach

All primary analyses will be performed on the Full Analysis Set.

Main primary analyses in maternal participants will include summaries of pregnancy outcomes and pregnancy related AESIs overall and by study arms. Pathways to preterm birth will be further broken down as: extremely preterm births (GA at birth: < 28 weeks); very preterm births (GA at birth: 28 - < 32 weeks); moderate to late preterm births (32 - < 37 weeks).

Main primary analyses in infant participants will include summaries overall, by study arms and by gestational age at birth (≥ 37 weeks or < 37 weeks; overall) of infant AESIs.

Primary endpoints will be reported by study arms while stratified by **CCI**

Pregnancy outcomes analytical approach:

The number and percentage of each pregnancy outcome is calculated among the maternal Full Analysis Set (for participants with medical records available), per pregnancy regardless of the number of fetuses in the concerned pregnancy.

The pregnancy related adverse events of special interest (AESIs) analytical approach:

The number and percentage of each pregnancy related adverse event of special interest is calculated based on the number of pregnancies reporting the symptom at least once. In addition, we will report the occurrence of pregnancy related adverse events of special interest. Only pregnancies based on medical record collection will be considered.

For infant participants, the infant participant reporting AESIs analytical approach:

The number and percentage of each neonatal adverse event of special interest is calculated based on the number of infants reporting the symptom at least once. In addition, we will report the occurrence of neonatal adverse events of special interest. Infants' data based on medical records only, will be considered.

CCI

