7.2. Participant discontinuation/withdrawal from the study

A participant may withdraw from the study at any time at the participant's own request for any reason (or without providing any reason).

A participant may be withdrawn at any time at the discretion of the investigator for compliance reasons. *Investigators may also withdraw participants from the prospective cohort who become a WONCBP as defined in Section 10.3.1.2 or receive bilateral tubal ligation during the prospective follow-up, if they do not plan to use any additional measures to attempt to conceive a pregnancy (e.g., sterilization reversal, or IVF).*

Investigators will attempt to contact participants who do not respond to or complete scheduled follow-up contacts.

All data collected up to and including the date of withdrawal of/last contact with the participant will be included in the study analyses. If the participant withdraws consent for disclosure of future information, the sponsor may retain and continue to use any data collected before such a withdrawal of consent.

The primary reason for participant discontinuation/ withdrawal from the study will be documented in the eCRF based on the list below:

- *Adverse event requiring expedited reporting (AESI and SAE) (prospective cohort only)*
- *Non-serious adverse event (MAE) (prospective cohort only)*

- Death
- Lost to follow-up
- Physician decision
- Protocol deviation
- Site terminated by Sponsor
- Study terminated by Sponsor
- Withdrawal by participant
- ***Migrated/moved from the study area***
- Other (specify).

Participants who are withdrawn from the study because of MAEs/SAEs must be clearly distinguished from participants who are withdrawn for other reasons. Investigator will follow participants who are withdrawn from the study due to a MAE/SAE until the event is resolved (see Section 10.2.3.5).

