3. ANALYSIS SETS

Table 2 Maternal Participants

| Analysis Set | Definition / Criteria | Analyses Evaluated |
|-------------------------|---|---------------------------------------|
| Screened | All participants who were screened for eligibility. | Study Population |
| Enrolled | All maternal subjects who completed the informed consent process and signed the informed consent form and were determined eligible for study participation. Note screening failures (who never passed screening even if rescreened) are excluded from the Enrolled analysis set as they did not enter the study. | Study Population |
| Full Analysis Set (FAS) | All maternal subjects who had pregnancy defined by this study (defined in the Protocol Section 5.1). | Primary, Secondary and other analyses |

Table 3 Infant Participants

| Analysis Set | Definition / Criteria | Analyses Evaluated |
|-------------------------|--|---------------------------------------|
| Enrolled Infant | Infants live-born to the maternal set, whose parents/LARs completed the informed consent process and signed the informed consent form. | Study Population |
| Full Analysis Set (FAS) | All infant subjects in the infant set who have post-delivery/birth data. | Primary, Secondary and other analyses |

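### SAP 4.2.2 and 4.3.1.2 set no follow-up condition, so prospective pregnancies lost before delivery and infants lost before Day 28 can count as event-free for pregnancy AESIs and neonatal death

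*SAP*

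**What the plan says.** SAP Section 3 defines the maternal Full Analysis Set as "All maternal subjects who had pregnancy defined by this study" and the infant set as "All infant subjects in the infant set who have post-delivery/birth data". Neither definition asks for a minimum length of follow-up.

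For the primary analysis, SAP 4.2.2 puts only one limit on pregnancy outcomes, the availability of records: "The number and percentage of each pregnancy outcome is calculated among the maternal Full Analysis Set (for participants with medical records available". Each pregnancy-related AESI is "calculated based on the number of pregnancies reporting the symptom at least once", with the restriction "Only pregnancies based on medical record collection will be considered". Infant AESIs follow the same pattern, with "Infants' data based on medical records only, will be considered". Only the numerator of the AESI percentage is explicit. SAP 4.3.1.2 carries the same AESI and infant rules over to the any-pregnancy analysis. The endpoint window in SAP 4.2 runs to Day 42 post-delivery.

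Two general rules bear on people who leave. Protocol 7.2 says "All data collected up to and including the date of withdrawal of/last contact with the participant will be included in the study analyses". SAP 4.1.1 says that, for a given participant, "missing or non-evaluable measurements will neither be imputed nor be replaced, and therefore will not be included in analysis". SAP 6.1.1 tabulates withdrawals and their reasons by arm. The text between SAP 4.2.2 and 4.2.4 is redacted; SAP 4.3.2.3 refers to Section 4.2.3 for sensitivity analyses.

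**The concern.** Take a prospective participant who withdraws at 18 weeks with antenatal records on file. She has a study pregnancy and medical-record data, so she meets every stated condition for the AESI analysis. She has reported no pre-eclampsia, chorioamnionitis or preterm labour, so under a count of events reported at least once she is a non-event. None of these was observed to be absent. Likewise, an infant with birth data who leaves on Day 3 belongs to the infant set and has no recorded death, although neonatal death is defined over the first 28 days (Protocol Table 30).

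By-arm incidence is the primary result of this study, and it follows a preterm-birth signal. Counting unobserved time as event-free lowers incidence, which is the unsafe direction. Protocol 4.5 records that participants already know which product they received, so unequal withdrawal is possible. It would carry into the by-arm percentages and, for selected endpoints, into the relative risks and p-values of SAP 4.3.2.2.

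**Working it through.** **Step 1. The plan's own precision figure.** SAP Section 5 gives a 95% Clopper-Pearson interval of 3.5% to 7% for an observed 5% among 650 participants. At 0.05 × 650 = 32.5 unrounded events, beta quantiles give 3.46% to 6.97%, which matches. (At the 33 events printed in SAP Table 5 the interval is 3.52% to 7.06%.)

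**Step 2. Which endpoints are exposed.**

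| Endpoint | Lost early: what the visible text does |
|---|---|
| Pregnancy outcome (live birth, stillbirth and so on) | Unclear. An unknown outcome is plausibly a missing measurement under SAP 4.1.1, but the stated restriction is only that records are available |
| Pregnancy-related AESI, including pathways to preterm birth | Exposed. Non-event by default unless reported before leaving |
| Neonatal death | Exposed between birth and Day 28 |
| Congenital anomaly diagnosed after leaving | Exposed in the same way |
| Infant preterm birth, small for gestational age, low birth weight | Not exposed. Fixed at birth, and a woman lost before delivery adds no infant to the denominator |

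Retrospective-cohort pregnancies had reached Day 42 post-delivery by enrolment (Protocol 5.1.1). The same holds for any pregnancy completed through Day 42 before enrolment and collected under Protocol 8.4.5.2. Only prospectively followed pregnancies can be lost in this way.

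**Step 3. Dilution.** Let p be the true risk and d the share of the whole denominator lost before the risk period and kept as non-events. Then reported rate = p × (1 − d). The documents give no withdrawal rate, so d is an assumption. Take p = 5%, the approximate lowest MAT-009 rate in SAP Section 5, as a reference value:

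- d = 2%: 5% × 0.98 = 4.90%
- d = 5%: 5% × 0.95 = 4.75%
- d = 10%: 5% × 0.90 = 4.50%
- d = 20%: 5% × 0.80 = 4.00%

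These are upper bounds on the dilution. Events recorded before leaving still count, and d is a share of all pregnancies in the denominator, including those that cannot be lost.

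**Step 4. Unequal loss with equal true risk.** Apparent RR = (1 − d in the vaccine arm) / (1 − d in the control arm).

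- 5% against 10%: 0.95/0.90 = 1.06; reversed, 0.90/0.95 = 0.95
- 5% against 15%: 0.95/0.85 = 1.12; reversed, 0.85/0.95 = 0.89

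**Step 5. At the planned size.** With 650 pregnancies and d = 10%, 65 are lost and 585 remain. About 0.05 × 585 = 29 events are seen. Kept as event-free: 29/650 = 4.5% (95% CI 3.0% to 6.3%). Complete follow-up only: 29/585 = 5.0% (3.3% to 7.0%).

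**Step 6. Does SAP 4.1.1 settle it?** It removes missing or non-evaluable measurements. An AESI that nobody reported is not plainly a measurement. If the rule were nevertheless read as dropping leavers without an event, leavers with an event would stay in and the bias would turn upward. Two programmers could produce different primary tables from the same text.

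**The case against.** A reader might infer that the plan counts all early leavers as event-free, and that every late-pregnancy and neonatal percentage, including the preterm-birth signal itself, is therefore understated. The documents do not support that. No sentence says leavers are event-free, and SAP 4.1.1 points the other way, most clearly for an unknown pregnancy outcome. Protocol 7.2 keeps the data collected up to withdrawal; it does not place the person in every denominator. Infant preterm birth, the endpoint closest to the signal, cannot be diluted by this route. Pregnancies completed before enrolment are not exposed. All of this stands, and it limits the point to prospectively followed pregnancies, pregnancy-related AESIs, neonatal death and late-diagnosed anomalies.

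Other objections stand in part. Withdrawals by arm will be tabulated, so an imbalance would be visible, but the tabulation does not correct the percentages. The outcome list in SAP 4.2.1 is open-ended, so an unknown-outcome row is not ruled out, but neither is it required. The redacted text where 4.2.3 would sit may deal with incomplete follow-up in a sensitivity analysis; the visible denominator wording in 4.2.2 would still need tightening. The size is modest: a fall from 5.0% to 4.5% lies well inside the planned interval of 3.5% to 7%. The analysis is descriptive, with no hypothesis tested.

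**Conclusion.** The point holds as a gap in the denominator rules rather than as a demonstrated bias. The visible text of SAP 4.2.2 and 4.3.1.2 does not prevent a prospective pregnancy with partial records, or an infant lost before Day 28, from counting as event-free for pregnancy-related AESIs or neonatal death. Applied literally, the AESI rule would do so by default.

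The relative understatement is at most the share lost before the risk period, so its size depends on a withdrawal rate that the documents do not give. The relative risks of 1.12 and 0.89 rest on an assumed 10-point difference in loss between arms. For pregnancy outcomes the defect is ambiguity only. The matter is worth settling before database lock, because the error would run towards reassurance in a safety study and the correction is cheap.

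**What to change.** Amend SAP 4.2.2 and 4.3.1.2 as follows.

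1. **Pregnancy outcomes.** Calculate percentages among pregnancies with a known end-of-pregnancy outcome, and show outcome unknown as a separate row by arm. Early endings tend to become known soonest, so this denominator can overstate early losses; the extra row lets the reader judge by how much.
2. **AESIs and neonatal death.** Keep every event recorded before withdrawal. Report by arm the number of pregnancies without records to the end of pregnancy and the number of infants without known vital status at Day 28. State how SAP 4.1.1 applies to an AESI not reported before withdrawal. Do not simply restrict the AESI analysis to pregnancies with complete records: a woman with documented gestational diabetes who then withdraws would be dropped together with her event, contrary to Protocol 7.2.
3. **Supporting analysis.** Add the cumulative incidence by gestational age for pregnancy AESIs, and by infant age for neonatal death, with withdrawal as censoring (Aalen-Johansen). This avoids both counting leavers as event-free and keeping only the leavers who had events. It assumes that those who leave have the same later risk as those who stay, which should be stated.

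The cost is a few derivation flags, some additional programming and slightly wider intervals. No new data collection is needed.
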